#### 3.2 STUDY OUTCOMES

The following outcomes measures are measured after index date (follow-up visits).

Table 3 Clinical outcomes of interest for objective 2 of the study

Variable Name	Туре	Description
Number of annualized asthma exacerbations 	Count	Annualized number of exacerbations requiring rescue steroids after index date
Asthma control in the past 4 weeks	Categorical	Categorized as controlled, partly controlled, or uncontrolled according to the GINA Asthma Control Criteria/Asthma Control Questionnaire (ACQ-6)/Asthma Control Test (ACT)
Total dose of oral corticosteroids 	Continuous	Label Dose X Frequency X Duration of Use for maintenance OCS between the index date and date of data extraction
Number of hospital admissions	Count	Annualized number of hospital admissions after index date
Number of emergency room visits	Count	Annualized number of emergency room visits after index date

<sup>3 Total number of exacerbations will be calculated between index date and current visit date

<sup>4 If use of SCS started after the index date, total dose will be calculated between start- and end date of use

#### 4. STATISTICAL ANALYSIS

[figure not shown]
#### 4.1 OBJECTIVE 1

Firstly, descriptive statistics of the baseline (pre-therapy) **Demographic and Clinical Variables** (section 3.1) for the five biologic utilization groups will be conducted for continuous and categorical variables accordingly.

- For variables measured on the interval or ratio scale, summary statistics produced will include:
  - Sample size (n)
  - o Percentage of the non-missing patients per variable
  - o Mean
  - Standard deviation (SD)
  - Range (minimum- maximum)
  - Median
  - o Inter-quartile range (25th and 75th percentile)
- For categorical variables, the summary statistics will include:
  - Sample size (n)
  - Range (if applicable)
  - Count and percentage by category (distribution)

[figure not shown]
Tables will be annotated with the total population size relevant to that treatment, including any missing observations.

In addition, to describing the groups of biologic usage, the extent of T2 phenotype will be demonstrated via applying the ISAR algorithm for T2/eosinophilic grades (Figure 2). The definitions of the grades were constructed per published evidence, asthma management guidelines and have gained ISAR steering committee consensus. The highest blood eosinophilic count ever (≥300, ≥150-300, <150 cells/µL), naïve or non-naïve biologic treatment including anti-IgE, anti-IL-5/5R and anti-il4/13 treatment, long-term OCS ever, elevated FeNO (≥25 ppb) ever, nasal polyps' diagnosis ever, and adult asthma onset (≥18 years) were parameters that facilitated the construction of the eosinophilic phenotype gradient. This methodology is in the process of publication in a peer-reviewed journal. Furthermore, the population will be described

in detail using demographics and clinical characteristics mentioned in table 2. When necessary, these characteristics will be broken down based on LTOCS use. Descriptive tables will be provided on demographics of the populations, biomarkers, asthma control and comorbidities.

First the demographic and clinical characteristics as mentioned in section 3.1 will be described in detail per group. This will include describing proportions on patients from each group based on their biomarkers, long term OCS (LTOCS) use, baseline demographics such as those outlined in Section 3.1. Next, the significant difference in level of T2 phenotypes and demographic or clinical characteristics (section 3.1) across the five groups will be compared and tested for statistical significance via Chi-square tests for comparison of counts data, and t-test or one-way analysis of variance (ANOVA) for continuous variables. Where appropriate, McNemar tests, paired t-tests will be considered. Statistical significance will be defined as p <0.05. Stata version 14.2 (College Station, TX, USA) will be used to conduct all statistical analyses and data manipulations.

Additionally, comparisons will be made as follows:

Study Protocol: [OPCG-2005] Biologic Usage Patterns, Clinical Outcomes and Healthcare Resource Utilization (CLEAR)

- 1. Switch vs. continue
- 2. Stop vs. continue
- 3. Patient received biologics vs. eligible but did not receive biologics
- 4. Biologic eligible (biologic users+ non-users but who qualify) vs. not eligible.

#### 4.2 OBJECTIVE 2

As there are various factors underpinning the probability of not receiving, receiving, continuing, switching, or stopping a biologic, comparing the clinical outcomes set forth in section 3.2 will need careful consideration. One of the main confounders to consider is the availability and/or accessibility of multiple biologics in a country. Therefore, all countries included in the analysis of assessing the clinical outcomes across biological utilization groups will have at least 2 biologics available in the market (availability defined as licensed in the country) at the time of the patient's enrolment into ISAR (index date). There will be a cut-off date of 01 Jan 2014 for assessment of clinical outcomes to ensure the availability of drugs in the market.

Furthermore, according to the results of objective 1 (pre-therapy or baseline characteristics), before assessing for differences in the clinical outcomes across groups, baseline imbalance will be examined across groups and matched accordingly. Prior to this step, the clinical outcomes of each group will be described.

Standardized mean difference (SMD) will be used to quantify differences in both continuous and categorical variables between the biologic utilization groups at baseline. An SMD  $\leq$  10% indicates sufficient balance between treatment groups. It is hypothesized that data completeness will vary between treatment groups. Therefore, propensity score matching methodology is envisioned at the stage of comparing between groups to conserve the statistical power. After the matching approach, the SMD will be recalculated to verify the accuracy of the model. If residual confounders are present, they will be entered into the respective multivariate model noted below. Clinical and/or health resource outcomes may be affected by the level of eosinophilic phenotypes, thus, results may be stratified by level of ISAR Eosinophilic Grade.

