# 3.STUDY VARIABLES AND STUDY OUTCOMES

Values captured closest to, and at/before index date of the following variables will be used to describe the biologic utilization groups (objective 1). Again, the index date refers to the date at which the initiation biologic was started or the date of ISAR enrolment for those who did not initiate any biologics.

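### The T2/eosinophilic grade uses biologic treatment as an input and is then tested between biologic initiators and non-initiators; its 'ever' inputs also have no stated index-date limit

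*Protocol*

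**What the plan says.** Section 4.1 lists the parameters behind the grade. They are "The highest blood eosinophilic count ever", in three bands; "naïve or non-naïve biologic treatment including anti-IgE, anti-IL-5/5R and anti-il4/13 treatment"; then "long-term OCS ever, elevated FeNO (≥25 ppb) ever, nasal polyps' diagnosis ever"; and adult onset of asthma. No time window is attached to any of the 'ever' items.

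The grade has two uses. First, Section 4.1 states that "the significant difference in level of T2 phenotypes and demographic or clinical characteristics (section 3.1) across the five groups will be compared and tested", with significance at p<0.05. Four further contrasts follow, among them "Patient received biologics vs. eligible but did not receive biologics". Second, Section 4.2 says of the clinical and resource outcomes that "results may be stratified by level of ISAR Eosinophilic Grade".

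The timing rule for baseline data is in Section 3: "Values captured closest to, and at/before index date of the following variables will be used to describe the biologic utilization groups". The list that follows is Table 2, and the grade is not in it. Sections 2.1 and 2.2 set the index date as the start of the first biologic for initiators and ISAR enrolment for the others.

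**The concern.** Extent of T2 phenotype is a named part of Objective 1 on the protocol's title page. If biologic treatment helps to determine the grade, then a grade difference between treated and untreated patients partly restates who was treated. A small p-value could not be read as evidence that the two populations differ biologically.

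The open-ended 'ever' inputs raise a second question. A highest-ever value tends to rise with the number of readings, and eosinophils, FeNO and OCS use can all change after a biologic is started or stopped. If post-index values enter, the grade is no longer a baseline characteristic, and stratifying post-index outcomes by it could create or hide associations.

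**Working it through.** The protocol gives no power or error figure for this analysis, so there is nothing to reproduce. The check is mainly one of definitions.

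**1. Treatment input and the index date.** Before the first biologic every patient is naive, and non-initiators stay naive. That leaves two cases:
- Status taken before index is the same for everyone and adds nothing.
- Status taken at or after index equals being an initiator.

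An at/before-index rule therefore cannot make this input both informative and independent of the grouping.

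**2. Which comparisons are touched.**

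| Comparison in Section 4.1 | Treatment status differs between sides? |
|---|---|
| Five-group test | Yes: three initiator groups, two non-initiator groups |
| Received vs eligible, not received | Yes, completely |
| Eligible vs not eligible | Partly: all initiators are on the eligible side, none on the other |
| Switch vs continue | No |
| Stop vs continue | No |

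**3. The 'ever' inputs.** Section 2.3 describes retrospective and prospective data, so post-index values exist. Section 3.2 measures outcomes after index, including maintenance OCS dose, and footnote 4 to Table 3 provides for steroid use that begins after index. Read literally, a patient who starts long-term OCS after index counts as long-term OCS ever.

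**4. Illustration of the treatment input (assumptions are not in the protocol).** Let the true high-grade share be p in both initiators and non-initiators, and let the input move a share q of lower-grade initiators up. The apparent share in initiators is p1 = p + (1 − p)q. Take N = 3,532 (Section 2.4), assume 300 to 1,000 non-initiators, and use a two-sided 5% test of two proportions:

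P(reject) = Φ[(|p1 − p| − 1.96·SE0)/SE1], with SE0 pooled and SE1 unpooled.

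Example: p = 0.60, q = 0.10, 600 non-initiators and 2,932 initiators. Then p1 = 0.64, SE0 = 0.0216, SE1 = 0.0219, and P = Φ[(0.04 − 0.0423)/0.0219] = 0.46.

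| q | p = 0.60 | p = 0.80 |
|---|---|---|
| 5% | 0.10-0.20 | 0.07-0.10 |
| 10% | 0.28-0.60 | 0.14-0.28 |
| 25% | 0.94-1.00 | 0.62-0.94 |

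Ranges run over 300 to 1,000 non-initiators. With no built-in shift the value would be 0.05.

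**5. Illustration of the 'ever' input (also assumed).** Lognormal eosinophil counts, population median 200 or 300, log-SD 0.8, within-patient correlation 0.5 or 0.7, no group difference and no treatment effect. The share whose highest count is at least 300:

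| Readings | Share |
|---|---|
| 1 | 31-50% |
| 2 | 42-67% |
| 3 | 48-75% |
| 4 | 52-80% |

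Within a scenario, going from two to three readings adds 6 to 9 percentage points.

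**The case against.** **The algorithm cannot be seen.** Being non-naive might raise the grade, lower it, or only govern how an on-treatment eosinophil count is read. This stands. The upgrade in the first illustration is an assumption, and neither the size nor the direction of any built-in difference is known. It does not remove the structural point that treatment status is an input to a variable tested between treated and untreated patients.

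**'Ever' may mean ever up to index.** Section 4.1 opens with baseline, pre-therapy variables, and Section 4.2 describes Objective 1 results in the same terms. This reading is reasonable. A reader might infer that the plan does condition on post-index data and puts an outcome into the stratifier. The text permits that but does not establish it. Long-term OCS at baseline is an ordinary Table 2 variable, and stratifying on it would be unremarkable. What stands is that the window is unstated.

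**Conflict with Section 3.** A reader might see a contradiction with the at/before-index rule. That rule is written for the Table 2 variables and the grade is not among them, so the documents leave a gap rather than contradict themselves.

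**Limited reach.** Outcome stratification is optional, and the grade is not named in the primary exacerbation model. Both stand. The Objective 1 test, however, is not optional.

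**Reading counts.** Nothing shows that groups differ as much as one reading against four, and Table S1 already records a highest count within the past year. Biologics also change eosinophils, so it does not follow that treated groups with more visits would look more eosinophilic. This stands as well.

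**Conclusion.** The point holds in a limited form. Biologic treatment is both a grade input and the grouping factor in the five-group test and in the received versus eligible-but-not-received contrast, and partly so in eligible versus not eligible. A reader might infer that every comparison of biologic-use groups is circular, but the documents do not support that, since continuers, switchers and stoppers have all been treated. Alongside this, the time window for the 'ever' inputs needs to be stated, because the literal wording admits post-index values into a possible outcome stratifier.

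The size of either effect cannot be computed from the protocol. The rejection rates and eosinophil shares above show only what could happen under the stated assumptions. The defect weakens interpretation of one named part of Objective 1. It does not by itself invalidate the primary exacerbation analysis.

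**What to change.** For the significance tests in Section 4.1, and for any stratification or matching in Section 4.2, define a version of the grade that (a) uses only values dated at or before the index date, so that 'ever' means ever up to index, and (b) leaves out the biologic-treatment input. Report the full consensus grade by group as a descriptive table without p-values.

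This is one re-derived variable and a wording change. Table S1 lists dates for eosinophil counts and FeNO tests and a start date for oral corticosteroids. No date for a nasal polyps diagnosis appears in the readable part of the appendices, so the rule for that item needs to be stated.

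The costs are that some patients will lack pre-index values and become ungradable, and that the tested grade departs from the algorithm agreed by the steering committee. The number ungradable should be reported by group.

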One of the promising ways of addressing all the severe asthma phenotypes may be via targeting one of the upstream inflammatory responses of the disease, such as the cytokine thymic stromal lymphopoietin (TSLP)[13]. TSLP is expressed by the airway epithelium in response to both allergic and non-allergic eosinophilic inflammation [14]. Lack of effective therapies for all patients with severe asthma, together with additional hurdles, such as accessibility or eligibility for more

Study Protocol: [OPCG-2005] Biologic Usage Patterns, Clinical Outcomes and Healthcare Resource Utilization (CLEAR)

than one biologic, have led to patients receiving sub-optimal or inappropriate biologics at initiation [11,12]. This can lead to various patterns of use, such as stopping or switching from the first biologic to a second, and in some cases, to a third or fourth biologic as clinicians and patients search deliberately for adequate response.

In an ISAR study on Biologic Utilization (prepublication) most patients (79%; 2791/3531) continued their first biologic, 10% (356/3531) stopped and 11% (384/3531) switched among patients who were followed up for at least a period of 6 months. This pattern was reproduced at the country level, although the ratio of 'stoppers' to 'switchers' varied. The most common reported reasons for stopping or switching a biologic was lack of efficacy benefits and/or adverse events. Disruption to the clinical management of biologics, most likely due to ineffective response and/or inappropriate initiation of the , may lead to a worsening of asthma control and an associated increase in health care utilization. This has yet to be demonstrated in a real-world setting or quantified. In addition, there may be a subgroup that is eligible yet is not reaping the benefits of targeted therapy.

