#### 2.4 FEASIBILITY

Optimum Patient Care Global
Study Protocol: [OPCG-2005] Biologic Usage Patterns, Clinical Outcomes and (CLEAR)

The diagram above shows the feasibility for the CLEAR study. Overall, 3,532 patients were eligible for the study. Most of them had initiated biologics and continued on them.

[figure not shown]

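### Section 4.1 compares continuous baseline variables by t-test or one-way ANOVA without naming an unequal-variance form; with very unequal groups, pooled versions would miss the 5% level if spreads differ

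*Protocol*

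**What the plan says.** Section 4.1 of the Protocol describes five utilization groups at baseline. T2 phenotype level and the section 3.1 characteristics "across the five groups will be compared and tested for statistical significance", using chi-square tests for counts "and t-test or one-way analysis of variance (ANOVA) for continuous variables". The threshold is fixed: "Statistical significance will be defined as p <0.05". Four two-group comparisons follow, among them "Switch vs. continue" and stop versus continue. McNemar and paired t-tests are mentioned for use where appropriate. No unequal-variance or rank-based alternative is named, and the variance form of the t-test is not given.

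The only group counts in the text are in section 1 (Background). They come from an earlier ISAR study of patients followed for at least 6 months: "most patients (79%; 2791/3531) continued their first biologic, 10% (356/3531) stopped and 11% (384/3531) switched". For CLEAR itself, section 2.4 says: "Overall, 3,532 patients were eligible for the study. Most of them had initiated biologics and continued on them". The split by group is in a diagram that is not reproduced.

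For the outcome comparisons, section 4.2 uses a different balance measure. The standardized mean difference (SMD) "will be used to quantify differences in both continuous and categorical variables between the biologic utilization groups at baseline", with a 10% threshold, and is recalculated after matching.

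**The concern.** A pooled-variance test uses one common variance for all groups. With equal group sizes, unequal spreads do little harm. With one large and one small group, the pooled variance is almost entirely that of the large group, while the true standard error of the difference is governed mainly by the small group. If the small group is more variable, the standard error is too small and the test rejects too often. If it is less variable, the test rejects too rarely. A larger total sample does not cure this, because the distortion depends on the ratio of sizes and the ratio of SDs.

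Equal spread cannot be taken for granted. The section 3.1 variables include blood eosinophils, IgE and FeNO, and Table 1 defines eligibility partly by thresholds on those markers. At stake are the p <0.05 flags that Objective 1 will report for continuous variables.

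**Working it through.** **Inputs.** Counts from the Background: 2,791 continued, 356 stopped, 384 switched. Their use for CLEAR is an assumption. Alpha is 0.05 (section 4.1), taken as two-sided because sidedness is not stated. The SD ratio r, small group to continuers, is an assumption; the range 0.5 to 2.0 is examined.

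**The plan's own figures.** 2,791 + 356 + 384 = 3,531. 2,791/3,531 = 79.0%, 356/3,531 = 10.1% and 384/3,531 = 10.9%, which agree with the printed 79%, 10% and 11%. The size ratios are 2,791/356 = 7.84 and 2,791/384 = 7.27.

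**Formula.** Set the continuers' SD to 1, with n1 the small group and n2 = 2,791.

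- Pooled variance: s² = [(n1 − 1)r² + (n2 − 1)] / (n1 + n2 − 2)
- Squared standard error used by the pooled test: A = s²(1/n1 + 1/n2)
- True squared standard error: T = r²/n1 + 1/n2
- True type I error: 2[1 − Φ(1.96·√(A/T))]

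**Stop versus continue, r = 1.25.** s² = (355 × 1.5625 + 2,790)/3,145 = 1.0635. A = 1.0635 × (1/356 + 1/2,791) = 0.003368. T = 1.5625/356 + 1/2,791 = 0.004747. √(A/T) = 0.842, so the pooled standard error is about 16% too small. 1.96 × 0.842 = 1.651, giving 9.9%.

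**r = 1.5.** s² = 1.1411, A = 0.003614, T = 0.006679, √(A/T) = 0.736, giving 14.9%.

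**r = 0.8.** s² = 0.9594, A = 0.003039, T = 0.002156, √(A/T) = 1.187, giving 2.0%.

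True type I error (%) of the pooled t-test; a dash marks a ratio not tabulated:

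| SD ratio | 0.5 | 0.8 | 0.9 | 1.0 | 1.1 | 1.25 | 1.5 | 2.0 |
|---|---|---|---|---|---|---|---|---|
| 356 vs 2,791 | 0.1 | 2.0 | 3.4 | 5.0 | 6.9 | 9.9 | 14.9 | 23.6 |
| 384 vs 2,791 | – | 2.0 | – | 5.0 | – | 9.8 | 14.7 | – |

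Simulation with 200,000 normal replicates per setting reproduces the 356 vs 2,791 row to within about 0.1 percentage point.

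**ANOVA, as an illustration only.** The planned omnibus test has five groups, but the text gives no counts for the two non-initiator groups, so only the three initiator groups can be simulated. If stoppers and switchers both differ from continuers, the error is 1.7% at r = 0.8, 10.7% at 1.25 and 16.8% at 1.5. If only stoppers differ, it is 3.3%, 8.1% and 11.8%.

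**Remedy checked.** Welch's t-test and Welch's ANOVA at the same sizes stay between 4.9% and 5.1% at every ratio from 0.5 to 2.0.

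**Cost when variances are equal.** Welch's degrees of freedom for 356 vs 2,791 are (1/356 + 1/2,791)² / [(1/356)²/355 + (1/2,791)²/2,790] ≈ 450, against 3,145 for the pooled test. The critical values are 1.965 and 1.961, which is a negligible difference in power.

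**The case against.** The strongest reply is that the protocol never says equal variances. A t-test may be pooled or Welch, the choice is a software option, and an analysis plan that is not shown may settle it. The four listed comparisons are all two-group, so the t-test is what matters for the main figures. This stands in part: one cannot say that the protocol prescribes a pooled t-test. It does not dispose of the point, because one-way ANOVA is named and pools by definition, and no alternative is offered.

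Three further objections stand and limit the point:

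- No baseline SD is given anywhere. A reader might infer that the error is 10% to 15%, or 2%, whenever the small group's spread differs. That is not so: a 10% difference in SD gives 3.4% or 6.9%. Nor do the documents show that stoppers or switchers are more variable. Baseline values are taken at or before the index date, before any treatment failure or adverse-event withdrawal.
- The counts belong to an earlier study. Section 2.4 supports marked imbalance in CLEAR but not a particular ratio. The figures cannot be carried over to the comparisons involving non-initiators or to the five-group test.
- Objective 1 is descriptive. Means, SDs, medians and quartiles are reported by group and do not depend on pooling, so any difference in spread will be visible.

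Because section 4.2 refers back to the Objective 1 results before matching, a reader might also infer that faulty p-values would carry into the outcome analyses. The text does not support that: balance is judged by the SMD before and after matching, and no step is tied to these p-values.

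**Conclusion.** The point holds as a conditional and minor one. The plan names a variance-pooling method (ANOVA) and a t-test of unstated form for groups that are likely to be very unequal in size. If the pooled form is used and the groups resemble the earlier registry counts, the true error of the stop-versus-continue test is about 10% to 15% at SD ratios of 1.25 to 1.5, about 2% at 0.8, and 3% to 7% at a 10% difference. Switch versus continue is nearly the same. The result rests on three assumptions: the borrowed counts, the SD ratios and the pooled form. The effect is confined to the Objective 1 p-values for continuous variables. The reported group differences, the SMD checks and the Objective 2 estimates are untouched.

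**What to change.** State in section 4.1 that continuous variables will be compared by Welch's t-test for two groups and Welch's ANOVA for more than two, or by linear regression with heteroscedasticity-robust standard errors. This is one sentence in the plan and a change of command or option in the analysis code. It needs no new data and no change to sample size or design.

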#### 2. STUDY DESIGN

#### 2.1 INCLUSION AND EXCLUSION CRITERIA

#### Inclusion criteria:

- Patients' data entries from ISAR who are from countries that have at least two biologics available (defined as the presence of a license for the treatment of severe asthma),
- Patients, 18 years of age or older, with a diagnosis of severe asthma which requires treatment with guideline-suggested medications with 2018 GINA:

Study Protocol: [OPCG-2005] Biologic Usage Patterns, Clinical Outcomes and Healthcare Resource Utilization (CLEAR)

- Treatment Step 4 and being uncontrolled OR
- Treatment Step 5.
- Registry data for a minimum of one year prior to index date (defined as the date of biologic initiation for biologic patients and date of ISAR enrolment for non-biologic patients) and 24 weeks after therapy or enrolment,
- Data received by ISAR before July 2021

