#### 3.1 DEMOGRAPHIC AND CLINICAL VARIABLES

Table 2 Demographic and clinical features to be described in Phase I of the study

Patient attributes	
Age	Age in completed years.
Sex	Female or Male.
Body Mass Index (BMI)	The ratio of weight (kg) to squared height (m  ). Categorised as underweight (< 18.5 kg/m  ), normal weight ( $\geqslant$ 18.5 kg/m  and < 25 kg/m  ), overweight ( $\geqslant$ 25 kg/m  and < 30 kg/m  ) and obese ( $\geqslant$ 30 kg/m  ).
Age of Asthma Onset	Age in completed years or months (if less than 1 year) at which asthma symptoms began. Early onset: <18 years of age; late onset: ≥18 years of age.
Smoking Status	Categorised as non-smoker, current smoker or ex-smoker; las ever.
Diagnostic Measurements	
Blood eosinophil count	Count of blood eosinophils (cells/uL).
Blood IgE level	blood level IgE (kU/L).
Predicted FEV1	Predicted value of forced expiratory volume in the first second of expiration (L).
Pre-bronchodilator FEV1	Measured forced expiratory volume in the first second of expiration, before the use of a bronchodilator (L).

Post-bronchodilator FEV1	Measured forced expiratory volume in the first second of expiration, after the use of a bronchodilator (L).
Pre-bronchodilator FVC	Forced vital capacity, before the use of a bronchodilator (L).
Post-bronchodilator FVC	Forced vital capacity, after the use of a bronchodilator (L).
Pre-bronchodilator FEV1/FVC Ratio	Measured FEV1 as a ratio of measured FVC.
Post-bronchodilator FEV1/FVC Ratio	Measured FEV1 as a ratio of measured FVC.
Fractional exhaled nitric oxide (FENO) test	Measurements of fractional nitric oxide concentration in exhaled breath, measured in parts per billion (ppb) at a flow rate of 50mL/s.
Skin Prick Test	Positive skin prick test
Therapy	
Long-term OCS	Maintenance oral corticosteroids (OCS)
Anti-IgE	Prescription for Anti-Immunoglobulin E (Anti-IgE)
Anti-IL5	Prescription for Anti-Interleukin 5 (Anti-IL5/5R)
Anti-IL4/13	Prescription for Anti-IL4/13
SCS-related comorbidities	Number of comorbidities reported from the following list: Anxiety, Depression, Osteoporosis, Diabetes, Peptic Ulcer, Pneumonia, Obstructive Sleep Apnea, Renal Failure, Heart Failure, Myocardial Infarction, Thromboembolism, Pulmonary Embolism, Serious infection (one or more). Other comorbidities based on availability of data.

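### The baseline list that feeds matching lacks prior exacerbations, prior admissions and emergency visits, country and index year, and the two-licence check is dated at enrolment instead of the initiator's index date

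*Protocol*

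**What the plan says.** Section 4.2 makes matching depend on the pre-therapy characteristics found under objective 1: "baseline imbalance will be examined across groups and matched accordingly". It then uses the SMD before and after propensity score matching, with 10% or less read as sufficient balance. Any residual confounders are to be entered in the outcome model, but none is named.

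Section 3 says what the objective 1 characteristics are: "Values captured closest to, and at/before index date of the following variables will be used to describe the biologic utilization groups (objective 1"). The variables that follow are Table 2, captioned "Demographic and clinical features to be described in Phase I of the study". They cover age, sex, BMI, age at onset, smoking, eosinophils, IgE, FeNO, spirometry, skin prick test, long-term OCS, biologic class and comorbidity counts.

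Exacerbations, admissions and emergency visits appear in Table 3 of Section 3.2, under the statement "The following outcomes measures are measured after index date (follow-up visits").

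On look-back, Section 2.1 requires "Registry data for a minimum of one year prior to index date".

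On access, Section 4.2 states: "One of the main confounders to consider is the availability and/or accessibility of multiple biologics in a country". Its remedy is to admit only countries with at least two licensed biologics, checked at the patient's "enrolment into ISAR (index date"), together with a 01 Jan 2014 cut-off for clinical outcomes.

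**The concern.** An SMD check can only find imbalance in the variables it is run on. Here the list tied to matching leaves out the history of the primary outcome, and also country and calendar time, through which access to biologics varies.

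Part of the imbalance is likely by design. Two or more pre-therapy exacerbations (or long-term OCS) are a condition in every column of Table 1. The note to Figure 2 treats all initiators as having met those criteria. The first outcome comparison in Section 4.2 sets initiators against all non-initiators, including those who are not eligible. So prior exacerbations help to define the groups being compared, yet balance on them is not among the stated checks. Objective 2 is also worded in terms of a reduction in exacerbations, which needs a pre-index value that neither Table 2 nor Table 3 lists.

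At stake is a statement of sufficient balance that does not cover exacerbation history or, within the included countries, differences in access and era. A separate fault is that the access restriction is tied to a date that conflicts with the protocol's own definition of index date.

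**Working it through.** **1. Is the list tied to matching?** Section 4.2 matches according to objective 1. Section 3 ties objective 1 to the variables listed there, and Section 4.1 refers to Section 3.1 for the baseline variables. The chain from Table 2 to matching is therefore in the text.

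**2. What is on the list?**

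| Variable | Table 2 | Elsewhere in the protocol |
|---|---|---|
| Prior-year exacerbation count | no | threshold of 2 or more in Table 1; post-index outcome in Table 3 |
| Prior admissions, emergency visits | no | post-index outcomes in Table 3 |
| Country | no | two-licence restriction (2.1, 4.2) |
| Index year | no | 01 Jan 2014 cut-off (4.2) |
| Number of biologics available | no | example of an interaction variable (4.2) |
| Asthma control | no | objective 1 descriptive tables (4.1) |
| Long-term OCS dose | use only | dose before and after therapy (4.2) |

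**3. Does the fallback catch the gap?** The residual-confounder step follows recalculation of the SMDs. If these are computed on Table 2 variables, imbalance in a variable outside Table 2 is not seen and does not trigger adjustment.

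**4. Index date.** Sections 2.1, 2.2 and 3 all set the index date at biologic start for initiators and at ISAR enrolment for non-initiators. Section 4.2 equates enrolment with index date for the licence check. That is correct for non-initiators and contradicts the other three sections for initiators. The gap can matter: Section 2.3 says ISAR holds retrospective data and began recruiting in December 2015. If 01 Jan 2014 is read as the earliest admissible date, a biologic could have been started up to about 23 months before any enrolment was possible (January 2014 to December 2015).

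**5. Size.** The protocol states no figure to reproduce. As an illustration, take a binary high prior-exacerbation history with prevalence p1 and p0 in the two groups and rate ratio RR for later exacerbations. The true group effect is a rate ratio of 1. All three inputs are assumptions.

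- Spurious rate ratio = (p1·RR + 1 − p1) / (p0·RR + 1 − p0)
- SMD = (p1 − p0) / √[(p1(1 − p1) + p0(1 − p0)) / 2]

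| p1 vs p0 | SMD | RR 1.5 | RR 2 | RR 3 |
|---|---|---|---|---|
| 55% vs 50% | 0.10 | 1.020 | 1.033 | 1.050 |
| 60% vs 50% | 0.20 | 1.040 | 1.067 | 1.100 |
| 60% vs 40% | 0.41 | 1.083 | 1.143 | 1.222 |
| 70% vs 40% | 0.63 | 1.125 | 1.214 | 1.333 |

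Example, last cell: (0.7 × 3 + 0.3) / (0.4 × 3 + 0.6) = 2.4 / 1.8 = 1.333. If the imbalance runs the other way, the reciprocals apply. In this illustration, holding the variable to the protocol's own 10% limit keeps the distortion to about 1.02 to 1.05. That protection is lost if the variable is not in the check.

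**The case against.** The strongest reply is that the protocol does not close the matching set. Table 2 is captioned as descriptive, Section 4.1 uses open wording when it refers to Section 3.1, propensity matching is only envisaged, and residual confounders may be added. The covariates of a propensity model are often left to an analysis plan, which is not at hand. This stands to the extent that the lack of a full covariate specification is no fault here. It does not remove the stated link from objective 1 to matching, or the gaps in the list to which that link leads.

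Several stronger readings are tempting, and the documents do not support them:

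- *Asthma control is ignored at baseline.* Section 4.1 says: "Descriptive tables will be provided on demographics of the populations, biomarkers, asthma control and comorbidities". Table 2 and Section 4.1 disagree and need reconciling.
- *Baseline OCS dose is ignored.* Section 4.2 summarises long-term OCS dose before and after therapy and models dose with GEE. Dose is missing only from Table 2.
- *Country and era are uncontrolled.* They are restricted, though coarsely.
- *Biologic class would enter the initiator score and separate the groups perfectly.* No section puts it there; the Table 2 rows may be purely descriptive.
- *Patients with no second biologic available at initiation are bound to be classed as continuers or stoppers.* Section 2.2 sets no limit on the time between biologics, so such a patient can still become a switcher later.

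It is also fair that matching on long-term OCS, biomarkers, lung function and comorbidity may reduce imbalance in prior exacerbations. By how much is unknown, and the stated check would not show it.

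**Conclusion.** The point holds in a limited form. The baseline list that Section 4.2 ties to matching has no prior-year exacerbation count, prior admissions or emergency visits, country or index year. Balance could therefore be declared without looking at the history of the primary outcome, or at access and era within the included countries. Separately, the licence check in Section 4.2 uses a date that contradicts the definition of index date for initiators in Sections 2.1, 2.2 and 3.

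The size of any bias cannot be taken from the documents. Under the stated assumptions it runs from 1.02–1.05 (SMD 0.10) to 1.13–1.33 (SMD 0.63). No single value in that range is an estimate for this study. A reader might also infer that the missing variables are the strongest predictors of outcome, or that every comparison is confounded. The protocol quantifies neither. It supports their relevance, because exacerbation is the primary outcome, prior exacerbations are part of eligibility, and access is named as a main confounder.

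**What to change.** - Add the 12-month pre-index exacerbation count, prior admissions and emergency visits, country and index year to Table 2, the propensity model and the SMD table. Country can be a covariate or stratum, or be represented by the number of biologics available.
- Keep the baseline exacerbation count as a covariate in the exacerbation models after matching.
- List asthma control in Table 2, and long-term OCS dose where recorded, to agree with Sections 4.1 and 4.2.
- State that the biologic-class rows of Table 2 are descriptive only for the initiator versus non-initiator comparison.
- In Section 4.2, apply the two-licence check at each patient's own index date as defined in Section 2.1.

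Most of this is wording and code, but it has a cost. Section 2.1 requires a year of registry data, not complete event counts, and Table S2 lists exacerbation dates and OCS label dose as bolt-on variables, so some values will probably be missing. More matching variables may also lose some patients. The stop and switch groups are the most exposed: the earlier ISAR work cited in Section 1 had 356 stoppers and 384 switchers among 3,531 initiators, and the title table lists 22 countries. For that reason exact matching on country is not required here. The number lost and the completeness of each added variable should be reported.
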